#### 8.4. Data Sources

The data used in this project will be retrieved via Statistics Denmark following a formal research request. Once approved Statistic Denmark can draw on data from registries under the Danish Health Data Authority.

### Unique Identifiers and Linkage Mechanisms

Danish registries are linked at the individual level primarily by the Civil Personal Register (CPR) number, a unique 10-digit personal identification number assigned to every resident at birth or immigration. The CPR number is used in all national databases that contain personal information, including health registers and socio-economic registers. This universal identifier functions as a common key that allows records from different databases to be matched for the same person with a high degree of accuracy. For example, a patient's hospital discharge in the National Patient Registry can be linked to that same person's prescription records in the Medicinal Product Statistics Register, and to their vital status in the Civil Registration System, by using CPR as the join field.

Other unique keys are used for non-personal linkages (e.g. a health facility ID, or family identifiers in certain datasets), but the CPR number is the cornerstone of data linkage. It enables both cross-sectional linkage (combining data across registers for a given year) and longitudinal linkage (tracking individuals over time). Because of CPR, "registers with information on health can be linked to other population registers containing information on, for example, education, income, housing, etc., at the individual level". This creates rich, multidimensional datasets for research, covering medical history, medication use, outcomes, and socio-demographics for each person.

Importantly, when data are prepared for research use, the actual CPR numbers are not revealed to analysts. Instead, Statistics Denmark (or the Danish Health Data Authority when relevant) replaces real CPRs with encrypted or pseudonymized IDs. In practice, each project gets a project-specific anonymous person identifier, so that researchers can link records internally within their dataset without ever seeing a real CPR number. This mechanism preserves the ability to link data accurately while protecting personal identity.

### **Registries utilized in this study:**

The Danish National Patient Registry (DNPR) holds information on inpatient visits (since 1977) and outpatient visits (since 1995), along with data on medical procedures, including hospital-administered biologics and phototherapy. Diagnoses are recorded based on the International Classification of Diseases (ICD-8 from 1977 to 1993 and ICD-10 from 1994 onward). Hospital-administered procedures and treatments are registered using the SKS codes, while surgical procedures have been recorded according to the NOMECCO Classification of Surgical Procedures (NCSP) since 1996.

The Danish Register of Medicinal Product Statistics contains information on all filled prescriptions at community pharmacies from 1995 onwards, using the Anatomical Therapeutic Chemical (ATC) classification system.

The National Cause of Death Registry holds information on the cause and date of death when applicable.

The National Population Registry contains demographic information, including vital status and gender.

### **Validation of registries and endpoints:**

The Danish registries are widely used in epidemiological research and known for their high-quality longitudinal data and validity of these. Input of data into the registries and the following use of this is managed by the Danish Health Data Authorities (Sundhedsdatastyrelsen); a public authority that follows national guidelines, laws and regulations. Specifically, the Danish Health Data Authorities manages all national health registries such as the CPR-registry, National Patient Registry, Hospital Medicines Registry etc.. Use of these data for research is handled via Statistics Denmark, as describes below.

A recent study successfully validated the ICD-10 AD diagnosis code in the DNPR^14. No formal validation studies of all study endpoints have been performed. However, the validity of cardiovascular diagnoses in the DNPR has been investigated and overall found to be high and sufficient for use in research since 2010^15. In addition, other studies have used these registries to investigate similar endpoints in a similar population. E.g. a large population-based cohort study demonstrated that the IRs of VTE, DVT, and PE in 17,341 patients with AD were comparable with those in the general population.

## **8.5. Study Size**

### **Study size and power calculations**

All patients meeting the inclusion criteria will be included for the current data analysis. Since this is a descriptive, retrospective study, no sample-size calculation is performed.

## **8.6. Data Management**

The raw data is already collected in structured form. The investigators will independently extract the data needed for the current retrospective based on the criteria set out in the protocol (section 9) using a unique identifier. All outcome analyses will be performed using SAS, R, and python.

The investigators operate in a secure, environment hosted at Statistics Denmark. Statistics Denmark's information security policy, which establishes the framework of the security work in Statistics Denmark and complies with the information security standard ISO 27001:2022 (Statistic Denmark Security Policy). The server is Windows-based and offers SAS 9.4, R 4.1.3, and python 3.7.4. The data are held at secure facilities by Statistics Denmark. All communication lines are encrypted, and security measures are updated on an ongoing basis, including ISO 2700x according to requirements from the Agency for Digitization ("Digitaliseringsstyrelsen") and the Center for Cyber security. Due to national data security

requirements, only results in the final analyzed report form can be provided to Pfizer (no access can be granted to source/raw data files or coding/logs). As for oversight, there will be regular interaction between Pfizer study lead and vendor to verify study progress and support with issue solving. Vendor management is supported by the Pfizer study manager to assure compliance and adherence to all processes and documentation required per Pfizer SOPs.

## 8.7. Data Analysis

### Raw data processing:

The raw data can be accessed remotely and online via The Secure Research Platform hosted in Statistics Denmark. Once a data request is submitted, Statistics Denmark will provide results in form of aggregated data. These results are organized as tables with columns and rows. Each column represents a variable (e.g., age, gender), and each row represents an observation or unit (e.g., dermatology verified AD patients receiving systemic treatment). The data may be numerical, textual, or categorical, depending on the type of variable.

Methods used to correct inconsistencies or errors:

If data points are missing for some individuals these cannot be added at a later point as the data received are anonymized and the source not identifiable. Any missing data will be noted in the analysis and added as limitations if it impacts the results and results presented. In case of too few patients or events in one drug group to carry out the planned analysis per group, the analysis can be carried out by combining drug classes.

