### Primary Objective:

The primary objective is to quantify the incident rate of major adverse cardiovascular events (MACE) and malignancy (excluding non-melanoma skin cancer (NMSC)) per individual conventional systemic treatment in a dermatologist-verified adult atopic dermatitis (AD) patient population.

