**Exclusion criteria rationale:**

The aim is to ensure that the adverse events registered cannot be attributed to any current or previous cases of cancer (criteria 1), other treatments (criteria 2 and 3), or other inflammatory diseases and their treatments (criteria 4). Additionally, it ensures that systemic treatments are administered specifically for AD and not for any other condition (criteria 4).

Given the high number of AD patients in the registry combined with previous experience each treatment group it is expected to comprise around 1000 patients for the majority of treatments.

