**Patient characteristics:**

Descriptive statistics will be presented to describe patient characteristics performed for all groups:

- a) dermatologist-verified adult patient population with atopic dermatitis (AD) receiving conventional systemic treatments as per inclusion/exclusion criteria,
- b) cohort-matched general Danish population
- c) cohort-matched patients with AD not receiving systemic treatment (see section above for matching criteria).

Categorical covariates will be described by frequency distribution while continuous covariates expressed in terms of their mean and standard deviation or median and interquartile range (IQR) as appropriate. The descriptive statistics will be captured in a statistical report with aggregated data in tables.

Between group comparisons for baseline characteristics:

Pearson's chi-square test will be used for dichotomous categorical variables, t-test will be used for continuous variables, and the Mann-Whitney U test for non-parametric variables. The statistical analysis will be captured in a statistical report with aggregated data in tables.

Primary endpoint statistical analysis:

Incidence rates of major adverse cardiovascular events (MACE) and malignancy (excluding non-melanoma skin cancer (NMSC)) will be presented per 10,000 person-years at risk with 95% confidence intervals. The incidence rates will be reported for each group separately: a) a dermatologist-verified adult patient population with atopic dermatitis (AD) receiving conventional systemic treatments as per inclusion/exclusion criteria, b) cohort-matched general Danish population and c) cohort-matched patients with AD not receiving systemic treatment (see section above for matching criteria). For group a, the incident rates will be presented per individual conventional systemic treatment (see table II).

In cases where patients received two systemic treatments or more during the data collection period, each treatment series will be analyzed independently. The statistical analysis will be captured in a statistical report with aggregated data in tables.

In the primary analyses, overlapping events will be attributed to the drug to which the patient has been exposed for the longest duration.

Secondary endpoint statistical analysis:

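### The sparse-data rule lets a pooled figure replace the per-drug primary incidence rate, which conflicts with the primary objective and is unnecessary for rates

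*Protocol*

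**What the plan says.** The primary objective (Protocol section 7) is a rate "per individual conventional systemic treatment in a dermatologist-verified adult atopic dermatitis (AD) patient population". The primary endpoint analysis in section 8.7 repeats this: "For group a, the incident rates will be presented per individual conventional systemic treatment (see table II". The statistic is simple. Rates "will be presented per 10,000 person-years at risk with 95% confidence intervals".

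Earlier in section 8.7, under Raw data processing, the protocol gives a rule for sparse data. It reads: "In case of too few patients or events in one drug group to carry out the planned analysis per group, the analysis can be carried". The remedy that the sentence names is pooling: "the analysis can be carried out by combining drug classes".

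The rule covers whatever is planned per drug and is not limited to one type of analysis. It does not say that the per-drug rate is still shown once drugs are pooled. Table II (section 8.3) puts five drugs under one conventional-treatment heading without sub-classes, so a pool could hold anything from two drugs to all five. On size, section 8.2 says each group is "expected to comprise around 1000 patients for the majority of treatments". It gives no size for the other treatments and no person-time for any drug.

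**The concern.** The primary question is asked drug by drug. A rule that allows a pooled answer when one drug is sparse allows that question to go unanswered for the drugs with the least safety information.

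Two consequences follow if the rule is applied to the rates. First, the pooled rate is an average weighted by person-time, so a raised or lowered rate in one drug is diluted by the others. Second, one of the two triggers is the number of observed events. Where that trigger decides, whether a drug is shown alone depends on its own result, and the drugs that remain visible tend to be those with high counts. Counts also differ by outcome, so a drug could appear alone for one outcome and inside a pool for another.

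The loss could not be repaired afterwards by the sponsor. Section 8.6 says that the sponsor receives only final report-form results, without raw data or code.

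**Working it through.** **Inputs from the protocol**
- About 1,000 patients for most drugs (section 8.2, exclusion criteria rationale).
- MACE about 1.5% per year, taken as 150 per 10,000 person-years (PY) (section 8.2, Representativeness).
- Myocardial infarction alone, 0.6% over 15 years, in a cited Danish hospital cohort (section 12, reference 27).
- Five drugs (Table II).

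**Assumptions, because the protocol gives no figure**
- 100 to 1,000 PY for the drug in question, and 1,000 PY at 150 per 10,000 for each other drug.
- Too few events means fewer than 5, with fewer than 10 as an alternative.

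**1. The protocol's own figure.** 13,000 × 0.015 = 195 MACE per year, consistent with its statement of over 100. That is for the whole AD cohort. For one drug, 1,000 × 0.015 = 15 per year of exposure.

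**2. Can a rate be given at a low count?** The exact limits for x events are χ²(0.025; 2x)/2 and χ²(0.975; 2x+2)/2, each divided by PY; the lower limit is 0 when x = 0. For x = 0 the upper limit is 3.69 events. Per 10,000 PY:

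| PY | Events | Rate (95% interval) |
|---|---|---|
| 100 | 0 | 0 (0 to 368.9) |
| 100 | 3 | 300 (61.9 to 876.7) |
| 1,000 | 0 | 0 (0 to 36.9) |
| 1,000 | 5 | 50 (16.2 to 116.7) |

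The interval may be wide, but it always exists.

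**3. Dilution.** Pooled rate = Σ wᵢ × rateᵢ, where wᵢ is the drug's share of pooled PY. Suppose the drug's own rate doubles from 150 to 300. With five drugs of 1,000 PY each: (4 × 150 + 300)/5 = 180.

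| Own PY | Pooled with four others: share, rate | Pooled with one other: share, rate |
|---|---|---|
| 100 | 2.4%, 153.7 | 9.1%, 163.6 |
| 500 | 11.1%, 166.7 | 33.3%, 200.0 |
| 1,000 | 20%, 180.0 | 50%, 225.0 |

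It works in the other direction too. A drug at 75 with 1,000 PY appears as (4 × 150 + 75)/5 = 135 in the five-drug pool.

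**4. How often would an event trigger fire?** P(X < k), with X Poisson of mean PY × rate. At 150 per 10,000 PY:

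| PY | Mean | k = 5 | k = 10 |
|---|---|---|---|
| 100 | 1.5 | 98.1% | 100% |
| 250 | 3.75 | 67.8% | 99.5% |
| 500 | 7.5 | 13.2% | 77.6% |
| 1,000 | 15 | 0.09% | 7.0% |

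The probability follows the drug's true rate. At 500 PY and k = 5 it is 67.8%, 13.2% and 0.09% for true rates of 75, 150 and 300. For a rarer outcome, 0.6%/15 = 0.04% per year gives about 0.4 infarctions in 1,000 PY, and the trigger fires in 99.99% of cases.

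**5. Selection among the rates still shown singly.** E[X | X ≥ 5] = μ × P(X ≥ 4)/P(X ≥ 5). At 250 PY and a true rate of 150, μ = 3.75, so 3.75 × 0.5162/0.3225 = 6.00 events, or 240 per 10,000 PY on average against a true 150. At 1,000 PY the average shown is 150.1, so the effect is negligible there.

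**The case against.** The strongest reply is that the rule applies only when the planned analysis cannot be carried out. If a rate with an exact interval can always be computed, the condition is never met for incidence rates, and the rule reaches only the Cox models. There would then be no conflict with the objective. This reading is possible, but the sentence does not say it. It names low event counts without limiting itself to models that can fail, and it covers the per-group analysis in general. A team could follow it in good faith and pool a primary rate.

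Other parts of the reply stand and limit the point:
- The wording is permissive. A reader might infer that per-drug rates will be replaced; the protocol only allows it, and nothing forbids showing both.
- The trigger is patients or events. A patient-count trigger does not depend on outcomes, so the selection argument applies only to the event trigger.
- A reader might infer that a pooled rate hardly reflects the drug's own risk. That holds for drugs with little person-time. At the protocol's own group size, with equal person-time, the share is 20% to 50%.
- The firing probabilities rest on an assumed threshold and assumed person-time. The primary endpoint in section 8.1 also includes malignancy, for which no rate is given, so MACE-only or infarction-only counts understate it.
- A numeric threshold, the pool definition and the interval method are commonly left to a statistical analysis plan. Their absence is not the point here.

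**Conclusion.** The point holds as a conflict within the protocol. The primary result is defined per drug, while the sparse-data sentence permits it to be pooled, partly on the basis of observed outcomes, without requiring the per-drug rate to be kept. The permission serves no purpose for incidence rates, since these can be computed at any count. It has a purpose only for the Cox comparisons.

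The size depends on use. With five drugs of equal person-time, a doubling from 150 to 300 would show as 180 per 10,000 PY; at 100 PY in the same pool it would show as 153.7. A reader might infer that pooling is likely throughout. At the protocol's 1.5% per year, an assumed 1,000 PY and an assumed threshold of five events, it would occur about 0.1% of the time. It becomes common for groups of 250 PY or fewer, or for outcomes as rare as the cited infarction risk. The protocol expects about 1,000 patients only for most drugs, so such cases are plausible, but it does not establish how often they would arise.

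**What to change.** Confine the pooling sentence in section 8.7 to the Cox comparisons, and add text to this effect:

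> Primary and secondary incidence rates are always reported for each Table II drug, with person-years and exact Poisson 95% confidence intervals, including when no event is observed. Rates over combined drugs are given in addition and never instead. If the Cox model cannot be fitted for a drug, its hazard ratio is reported as not estimable; any pooled hazard ratio is labelled supplementary.

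Where data-release rules bar a small count, mark that cell as suppressed. Giving the upper limit with the person-years would not protect it, because together they determine the count.

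The cost is a short text change and a few more table rows. The downside is that some per-drug intervals will be visibly wide: with 100 PY and no events, for example, the upper limit is 368.9 per 10,000 PY.

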### Treatment series

Treatment series are defined as periods of time in which a patient is considered on active treatment. The allowable gap between administrations of the same drug is 150 days to aggregate the treatment series. If the gap exceeds 150 days, patients are considered to have initiated a new treatment series. The allowable gap is based on the common gap of 90 days between each filled prescription, with an additional extension of 60 days to mirror the design of ORALSURV, which allowed for up to 2 months of discontinuation for safety issues.

The duration of active therapy following the last filled prescription or administration is set at 120 days, reflecting the standard 90-day prescription interval plus an additional 30 days, as outlined by Fleischmann et al. . Each treatment series is considered separately, as concomitant therapies were allowed in the ORALSURV study design.

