#### Secondary endpoints

Reporting of detailed event-by-event incidence rates

- All-cause mortality
- Arterial thromboembolisms
- Venous thromboembolisms
- Dyslipidemia
- Herpes zoster
- NMSC
- Serious infections
- MACE [primary]
- Malignancies (excl. NMSC) [primary]

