### Follow-up and exposure and censoring

Patients are followed from the index date until the earliest occurrence of one of the following: the event of interest, the study closing date (30 December 2022), initiation of a

biological therapy or JAK inhibitor, death, the development of a condition that would qualify for one of the treatments of interest (Table 1), or migration.

When using treatment series, exposure time is calculated and cumulated based on the specific therapy received. Except for the event of interest, any of the previously mentioned cases will result in censoring.

Additional analyses will be conducted on an intention-to-treat basis.

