## Events

During the treatment series, an adverse event can be adjudicated to the ongoing treatment. In the intention-to-treatment (ITT) study design, the event can be adjudicated to the treatment initiated at the index date.

If a patient is receiving overlapping treatments, any adverse event occurring during both therapies will be adjudicated to the therapy the patient has been on for the longest duration. Such events are referred to as overlapping events.

In the primary analyses, for overlapping events, the event is assigned to the drug the patient has been on the longest.

Multiple sensitivity analyses will be conducted to address overlapping events:

- The event is assigned to the most recent drug.
- The event is attributed to both drugs.
- The event is attributed to neither drug and the patient is censored.

Serious infections are defined as those requiring hospital admission for more than one day (Table V), and infections with HIV, hepatitis B or C, tuberculosis, or infections resulting in death.

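### The 150-day bridging gap and the 120-day tail make exposure on days 121-150 depend on a later refill, which biases series-based rates of fatal outcomes slightly downward

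*Protocol*

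**What the plan says.** Protocol section 8.7, under Treatment series, sets two lengths.

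- **Bridging:** "The allowable gap between administrations of the same drug is 150 days to aggregate the treatment series". It is measured from fill to fill: "The allowable gap is based on the common gap of 90 days between each filled prescription, with an additional extension of 60 days". Beyond that, "If the gap exceeds 150 days, patients are considered to have initiated a new treatment series".
- **Tail:** "The duration of active therapy following the last filled prescription or administration is set at 120 days", built from the 90-day prescription interval plus 30 days.

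All time inside a series is exposed: "Treatment series are defined as periods of time in which a patient is considered on active treatment". The next two subsections draw both parts of the rate from the series. For the denominator, "When using treatment series, exposure time is calculated and cumulated based on the specific therapy received". For the numerator, "During the treatment series, an adverse event can be adjudicated to the ongoing treatment".

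The fatal outcomes concerned are "All-cause mortality" (a secondary endpoint, section 8.1) and cardiovascular death, which Table III lists as part of MACE. An intention-to-treat analysis is planned as an additional analysis. The listed sensitivity analyses cover overlapping events, inclusion after a single fill, calendar periods and inverse probability weighting. None varies the gap or the tail.

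**The concern.** The two lengths differ by 30 days, and what fills that difference is decided by the patient's future. If a refill comes on days 121-150, the days from 121 to the refill are active treatment. If no refill comes by day 150, the series closed on day 120 and anything later is off treatment. Whether a given day counts should be known on that day; here it is not.

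For death this is immortal time in the strict sense, because a patient must survive to the refill for the window to count. For myocardial infarction, stroke, malignancy or serious infection, the event is lost only if it prevents a refill by day 150.

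The matched cohorts have no fill-based series, so the error does not cancel in the tertiary comparisons. It leans towards making treatment look safer in a study whose main output is a rate per drug, and a larger sample does not shrink it.

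**Working it through.** **Inputs from the protocol**
- Gap: 90 + 60 = 150 days; tail: 90 + 30 = 120 days (section 8.7). Both sums reproduce the stated figures. The window is 150 − 120 = 30 days.
- Illustrative rate: 1.5% per year, or 150 per 10,000 person-years (section 8.2, the MACE expectation).
- About 1000 patients for most treatments (section 8.2, exclusion criteria rationale).

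**Assumed, because the protocol does not give them**
- Refill intervals: lognormal, median 90 or 110 days, log-SD 0.15, 0.25 or 0.40; 8% of fills are the last.
- s, the probability that an event in the window prevents a refill by day 150: 1 for death; 0, 0.5 or 1 for non-fatal events.

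**Step 1. Two patients with a fill on day 0.** The first refills on day 140. The gap is within 150, so days 121-140 are exposed. The second dies on day 130. Day 0 was the last fill, the series ended on day 120, and the death is not counted.

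**Step 2. Formula.** With a constant low hazard,

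expected observed rate / true rate = 1 − s × f,

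where f is the share of counted exposure that lies beyond day 120 in bridged intervals.

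A hand example: 10% of intervals reach 135 days (15 days in the window) and the rest last 90 days. Then f = 0.10 × 15 / (0.90 × 90 + 0.10 × 135) = 1.5 / 94.5 = 0.016, and the death rate is 1.6% too low.

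**Step 3. Range.** f was computed over 1,000,000 simulated intervals per row. The last column applies the ratio for s = 1 to 150 per 10,000 person-years.

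| Median interval | log-SD | Ratio, s = 1 | Ratio, s = 0.5 | 150 becomes (s = 1) |
|---|---|---|---|---|
| 90 days | 0.15 | 0.998 | 0.999 | 149.7 |
| 90 days | 0.25 | 0.989 | 0.994 | 148.3 |
| 90 days | 0.40 | 0.983 | 0.991 | 147.4 |
| 110 days | 0.15 | 0.978 | 0.989 | 146.7 |
| 110 days | 0.25 | 0.973 | 0.986 | 145.9 |
| 110 days | 0.40 | 0.976 | 0.988 | 146.5 |

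With s = 0 the ratio is 1 throughout. A separate simulation of deaths with gamma intervals and 12% stopping per fill agrees: 0.6-1.6% too low at a mean of 90 days (SD 20-45), 2.5% at 110 days (SD 35) and 3.2% at 120 days (SD 30).

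**Step 4. Ceiling from the protocol's figures.** If every refill came on day 150 and s = 1, f = 30/150 = 0.20. The ratio is 0.80, and 150 becomes 120.

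**Step 5. With equal lengths.** Using 150/150 or 120/120, the ratio is 1.0000 in every row, because exposure on any day then depends only on past fills.

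**Step 6. Against precision.** 1000 person-years at 1.5% give 15 events, with an approximate relative 95% half-width of 1.96/√15 = 51%. With 100 events it is 1.96/√100 = 20%.

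**The case against.** The strongest objection is size. The only refill figure in the protocol is 90 days, where the bias is at most about 1.7%, or about 2.6 per 10,000 person-years on a rate of 150. Against a half-width of 20-51%, that is unlikely to change any conclusion; a 1.6% bias would match the half-width only at about (1.96/0.016)² ≈ 15,000 events. This stands, and it limits how much weight the point can carry.

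Two mitigations are fair to note. The intention-to-treat analysis does not use gap or tail. It is only additional, however, and answers a different question. Each length also has its own cited rationale: a JAK-inhibitor trial in rheumatoid arthritis for the gap and a post hoc safety analysis for the tail. Neither rationale addresses using the two lengths together.

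Three stronger readings are tempting, and the protocol does not support them.

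- **That the window is immortal for every outcome.** It is so only for death. For non-fatal events the bias is nil if refilling is unaffected, and the protocol gives no figure for that. Building series only from fills before the event would make the window event-free for all outcomes, but the protocol does not say this is done.
- **That the ranking of drugs is distorted.** No drug-against-drug contrast is planned, and no refill pattern by drug is given.
- **That rates could really be 20% too low.** That needs every refill to fall on day 150.

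**Conclusion.** The point holds in a limited form. As written, the two lengths make exposure on days 121-150 conditional on a refill by day 150. The direction is certain for all-cause mortality and for cardiovascular death within MACE: series-based rates in the treated group are too low, and comparisons with both matched cohorts lean the same way. For MACE as a whole the relative bias is no larger than for death alone, and smaller if some patients with infarction or stroke still refill in time.

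The likely size is 0.2-1.7% for fatal outcomes at 90-day intervals and about 2-3% at 110-120 days. Both ranges assume a constant hazard and a refill distribution that the protocol does not supply. The bias is small beside the expected random error, but it is systematic, no planned sensitivity analysis would show it, and it is cheap to remove. It should be corrected; it does not threaten the study.

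**What to change.** In section 8.7, set one length for both the bridging gap and the tail. Every fill or administration, last or not, then gives the same fixed exposed window, cut short only by a new fill, an event or censoring. Either length removes the bias. Report the other one (120 or 150 days for both rules) as a sensitivity analysis. Using a single length also keeps the definition of a series as time on active treatment intact, which would fail if 150 days still joined fills but only 120 days counted as exposed.

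The cost is a short change of text, one constant in the code and one extra run. With 120 days there is slightly less person-time, and a refill on days 121-150 starts a new series, which also restarts the duration used to attribute overlapping events. With 150 days there is slightly more person-time after last fills. Either choice departs from one of the two cited conventions, and the text should say so.
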